# Earliest lesion assessment date among target, non-target and new lesions at which visit identified as disease progression by central reviewer.

**Tumor response (CR, PR, SD, PD) at Week 12 and Week 28**

Tumor response (CR, PR, SD, and PD) will be evaluated by central imaging assessment at Week 12 and Week 28 as defined by the IWG Criteria 2007.

**16.2.2. MISSING DATA METHODS FOR SECONDARY EFFICACY VARIABLE(S)**

All analyses of secondary efficacy variables will be based on available data. No missing data will be imputed.

---

Document:

Author:

Version Number:

Version Date:

Final v1.0

10Sep2019

Template No: CS\_TP\_BS016 Revision 4

Effective Date: 01Apr2016

Reference: CS\_WI\_BS005

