2.3.2 Secondary Efficacy Endpoints

Tumor response evaluations as defined by the revised IWG Criteria 2007, for malignant lymphoma (Appendix 4):

- ORR at Week 12
- Complete Response (CR) at Weeks 12 and 28
- Partial Response (PR) at Weeks 12 and 28
- Stable Disease (SD) at Weeks 12 and 28
- Progressive disease (PD) at Weeks 12 and 28
- Time to event (TTE), defined as the time from the date of randomization to the date when an event occurs; an event is disease progression, death due to any cause, or the start of new treatment for FL, whichever comes first

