ADR adverse drug reaction; AE adverse event; AESI adverse event of special interest; ALT alanine aminotransferase; AST aspartate aminotransferase; BUN blood urea nitrogen; BSA body surface area; CR complete response; CT computerized tomography; DNA deoxyribonucleic acid; ECG electrocardiogram; ECOG Eastern Cooperative Oncology Group; EOS End of study; FACS fluorescence-activated cell sorting; FL follicular lymphoma; HACA human antichimeric antibody; HBcAb hepatitis B core antibody; HBsAg hepatitis B surface antigen; HBV hepatitis B virus; HCV hepatitis C virus; HIV human immunodeficiency virus; i.v. intravenous; IWG International Working Group; IXRS Interactive Voice Telephone and Web Response System; LDH lactate dehydrogenase; PCR polymerase chain reaction; PD pharmacodynamics; PE physical examination; PET positron emission tomography; PML progressive multifocal leukoencephalopathy; PK pharmacokinetic; SAE serious adverse event; TB tuberculosis; WHO World Health Organization.

- a Most screening assessments should be conducted within 30 days of Day 1. However, the screening CT scan and bone marrow biopsy may be conducted within 60 days before randomization. The total screening period is not to exceed 60 days in this case.
- b Patients who withdraw consent from the study will have no further investigations performed after their withdrawal.
Patients who discontinue study drug early will have investigations performed as indicated in footnote c (Early treatment discontinuation visit).
All other patients will continue to attend visits until Week 52 to obtain PK, PD, safety, efficacy, and immunogenicity data.
- c Patients who discontinue treatment at any time during the study after Day 1 (but do not withdraw their consent) will be required to have efficacy assessments at Week 28, or before a new anti-lymphoma treatment is started, and an early treatment discontinuation visit. If new treatment must be started before the Week 28 assessments, then the early treatment discontinuation visit, including a CT scan, should be performed before the start of the new treatment.
- d Unscheduled visits should be scheduled as per Investigator discretion. Table shows an example of assessments. Tests will be selected as per Investigator's discretion.
- e Inclusion and exclusion criteria to be re-checked on admission to the study site.
- f Body weight measurement required for BSA calculation; body weight is measured as part of the complete PE at other visits.

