4.11.2 Prohibited Treatments

Treatment with any other experimental drug or a concomitant chemotherapy, anticancer hormonal therapy, radiotherapy, or immunotherapy is prohibited during study participation. This includes additional doses of rituximab or SAIT101 after the initial 4-weekly doses.

If a patient requires tumor targeting treatment for FL other than the protocol-defined treatment with rituximab or SAIT101 monotherapy due to disease progression based on tumor assessments done at investigational site, he or she will be considered as a treatment failure and should be discontinued from the study treatment. (See Section 3.3.1.2) Patients with progressive disease should be treated with an adequate therapy according to judgment of the treating physician. In such case, patient will be followed-up until Week 52 (EOS) for safety and immunogenicity.

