8.8 Efficacy Analyses

The statistical analysis of the primary endpoint for this study will be performed after the last patient has completed the Week 28 response assessment. All efficacy data will be analyzed at this time, plus all PK, PD, immunogenicity, and safety data available at the time of data

cut-off, and these data will be reported in the CSR (Week 28 CSR). After the last patient has completed Week 52 of the study, a CSR addendum (Week 52 CSR) will be prepared to report the additional safety data.

Efficacy will be assessed centrally as CR, PR, SD, and PD, as defined in IWG criteria 2007, and TTE. The main efficacy endpoint will be the difference in ORR (CR+PR) at Week 28, approximately 24 weeks after the completion of study treatment. The efficacy analyses will be applied for both the PP set and FAS. FAS will be considered as primary efficacy analysis population and analysis in PP set will be conducted as a sensitivity analysis.

In FAS, patients without a response assessment at Week 28 will be handled using a conservative approach by imputation using drop-out reason (IUDR), where Non-responder imputation (NRI) method in case of treatment related reasons and otherwise multiple imputation (MI) procedure assuming missing at random (MAR) will be applied. For the PP set, all available data will be used for analysis.

Potential withdrawal reasons are considered as follows based on previous studies; The major reason of missing response assessment at Week 28 is assumed to be either the start of new treatment of FL due to lack of efficacy or toxicity based on Ardeshtna et al. In such reasons related to treatment (i.e. treatment failure requiring tumor targeting treatment for FL other than the protocol-defined treatment, death due to progressive disease), patients without a response assessment at Week 28 will be handled as non-responders. Missing responses unrelated to treatment (i.e. withdrawal by subject, pregnancy) as seen in the Colombat et al. would be considered ignorable missing at random (MAR) and multiple imputation procedure using logistic regression method will be used to impute the missing response assessment at Week 28 (responder versus non-responder). No imputation will be applied when the reasons are unknown whether they are related to treatment or not (i.e. lost to follow-up).

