## 5.3. RETESTS AND UNSCHEDULED VISITS DATA

Generally, data recorded at the nominal visit will be presented for by-visit summaries.

Unscheduled measurements will not be included in by-visit summaries, but will contribute to the best/worst case value where required (e.g. shift table).

In the case of a retest (same visit number assigned), the latest available measurement of non-PK/PD assessments for that visit will be used for by-visit summaries.

If the patient discontinued treatment during the study after Day 1 and the next visit data is missing, then early termination data, i.e. early treatment discontinuation visit data, will be mapped to the next available visit number for by-visit summaries. Otherwise, early termination data will not be mapped.

Listings will include scheduled, phone visit, unscheduled, retest and early study discontinuation data in chronological order. Listings will include all scheduled, unscheduled, retest, early discontinuation and phone visit data.

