### **16.1.3. ANALYSIS OF PRIMARY EFFICACY VARIABLE**

The primary test for statistical equivalence will be performed with respect to SAIT101 versus MabThera® for patients in the FAS. The primary hypothesis is based on the difference in ORR at Week 28 between the two treatments. The equivalence will be declared if the 2-sided 95% CI of the difference in the ORR at Week 28 between treatments (SAIT101 versus MabThera®) is contained within the equivalence margin of [-16.0%, 16.0%] by Cochran-Mantel-Haenszel (CMH) tests. The adjusted proportion difference in ORR and its 95% Newcombe-Wilson CI will be calculated using weighted CMH with stratification factor FLIPI-2 (low, intermediate and high risk).

Descriptive statistics will be presented for the ORR as well as the overall tumor assessment (CR, PR, SD, PD) at planned time points by treatment groups. In addition, a listing of target, non-target and new lesions assessed per IWG criteria 2007 by visit will be also presented.

A bar-chart plot presenting the overall tumor response rate (CR, PR, SD and PD) and the ORR at Week 12 and Week 28, by treatment group, will also be provided.

---

Document:

Author:

Version Number:

Version Date:

Final v1.0

10Sep2019

Template No: CS\_TP\_BS016 Revision 4

Effective Date: 01Apr2016

Reference: CS\_WI\_BS005

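### Week 28 response categories rest on available data with no rule that keeps an earlier progression as progression, so some early progressors can drop out of the progression rate

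*SAP*

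**What the plan says.** Protocol 2.3.2 lists each response category as a secondary endpoint, including "Progressive disease (PD) at Weeks 12 and 28". SAP 16.2.1 adds: "Tumor response (CR, PR, SD, and PD) will be evaluated by central imaging assessment at Week 12 and Week 28". SAP 16.1.3 plans descriptive statistics for "the overall tumor assessment (CR, PR, SD, PD) at planned time points by treatment groups", and one bar chart showing the categories and the ORR at both visits.

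The missing-data rule for all secondary efficacy variables is in SAP 16.2.2: "All analyses of secondary efficacy variables will be based on available data. No missing data will be imputed".

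Four other provisions decide who has a Week 28 result:

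- Protocol Table 1, footnote c: patients who stop treatment are "required to have efficacy assessments at Week 28, or before a new anti-lymphoma treatment is started".
- Protocol 4.11.2, on patients who need other treatment because of progression: "In such case, patient will be followed-up until Week 52 (EOS) for safety and immunogenicity".
- SAP 5.3: "Unscheduled measurements will not be included in by-visit summaries". The same section moves early treatment discontinuation data to the next available visit number when the patient discontinued treatment and the next visit is missing. Otherwise such data are not moved.
- Protocol Table 1, footnote k, and SAP 16.1.1: a CT from 4 weeks before to 2 weeks after the Week 12 or Week 28 visit is permitted.

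**The concern.** The Week 28 result can be missing because of the outcome it is meant to measure. Protocol 8.8 says so itself, in a sentence that goes on to name inefficacy or toxicity: "The major reason of missing response assessment at Week 28 is assumed to be either the start of new treatment of FL due to". An available-data rule is then not neutral. It tends to remove failures from the table, which lowers the PD rate and, if percentages are based on assessed patients, raises CR and PR.

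Two things are at stake. First, the Week 28 categories may not agree with the primary ORR, although SAP 16.1.3 puts both in one chart. SAP 16.1.2 scores a patient who starts new treatment for treatment-related reasons and has no Week 28 assessment as a non-responder, whereas the category table may simply omit that patient. Second, if the loss differs between arms, the table can show or hide a difference in progression. In a biosimilarity trial, readers will look at that row.

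**Working it through.** **Step 1. The plan's own figure.** The only related calculation in the documents is the power for ORR. Inputs from SAP 2.3: 154 per arm, ORR 77% in both arms, margin ±16%, two-sided 95% Newcombe-Wilson interval.

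- Exact binomial enumeration gives 84.0% at 154 per arm (stated 83%) and 81.3% at 147 per arm (stated 80%).
- The normal approximation, 2Φ(0.16/√(2 × 0.77 × 0.23/154) − 1.96) − 1, gives 83.1%; with 147 per arm it gives 80.6%.

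The stated power reproduces, and nothing below changes it.

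**Step 2. Where an early progressor ends up.**

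| Patient who then starts new treatment | Week 28 category table | Primary ORR, no Week 28 assessment (SAP 16.1.2) | Time to event (SAP 16.2.1) |
|---|---|---|---|
| Central PD on the scheduled Week 12 CT | PD appears at Week 12; nothing carries it to Week 28 | Non-responder | Event |
| Central PD on an unscheduled CT outside the Week 28 window | Kept out by SAP 5.3 | Non-responder | Event |
| Central PD on the early treatment discontinuation CT | Unclear: may be mapped to Week 20, which has no CT, or to Week 28 | Non-responder | Event |

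The third row has a further uncertainty. Dosing ends on Day 22, and SAP 5.3 applies to patients who discontinued treatment. It does not say whether a patient who received all four infusions and progressed later is covered.

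**Step 3. Size in one arm of N = 154.** Let k be the number of earlier progressors without a Week 28 result, and s the number with PD on an actual Week 28 scan. Neither is given in the documents, so both are assumed. For scale, 4% of 154 is 6.2, or about 6 patients. That 4% (SAP 2.3) covers drop-outs and major deviations together and is not a rate of early progression.

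- Available-data PD rate = s/(N − k)
- PD rate with earlier PD kept = (s + k)/N

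| k | s | Available data | Earlier PD kept | Understatement (points) |
|---|---|---|---|---|
| 3 | 8 | 8/151 = 5.3% | 11/154 = 7.1% | 1.8 |
| 3 | 15 | 15/151 = 9.9% | 18/154 = 11.7% | 1.8 |
| 6 | 8 | 8/148 = 5.4% | 14/154 = 9.1% | 3.7 |
| 6 | 15 | 15/148 = 10.1% | 21/154 = 13.6% | 3.5 |
| 15 | 8 | 8/139 = 5.8% | 23/154 = 14.9% | 9.2 |
| 15 | 15 | 15/139 = 10.8% | 30/154 = 19.5% | 8.7 |

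Differences are taken before rounding. Using all 154 as denominator without keeping the earlier PD does not help the PD row: 8/154 = 5.2% and 15/154 = 9.7%.

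**Step 4. CR+PR.** With 119 responders (119/154 = 77.3%) and k = 6, a denominator of assessed patients gives 119/148 = 80.4%.

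**Step 5. Comparison of arms.** Suppose 18 patients progress in each arm (18/154 = 11.7%), and 3 in one arm and 9 in the other lack a Week 28 result. The table shows 15/151 = 9.9% against 9/145 = 6.2%, a difference of 3.7 points where none exists.

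**The case against.** The case on the other side has real force.

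- **Scans may be recovered.** CT is scheduled only at screening and Weeks 12 and 28, so for tumour response the next available visit in SAP 5.3 can be read as Week 28. A pre-treatment CT showing PD would then appear there. Scans inside the permitted window can also serve as the visit scan. A reader might infer that all early progressors vanish from the Week 28 table; the documents do not support that. What remains is PD on the Week 12 scan, PD on an unscheduled scan outside the window, and an unclear mapping.
- **The denominator is not stated.** Protocol 8.8 says efficacy variables are summarised for the FAS and PP set, and SAP 7 leaves table content to templates outside these documents. If percentages already use the full set, CR and PR are not inflated. That part of the point is conditional. The loss from the PD count is not, because a larger denominator does not restore the missing events.
- **The information is not lost to the trial.** Time to event has Kaplan-Meier curves, a hazard ratio and a listing, and the primary analysis counts these patients as non-responders. This stands. However, time to event combines progression, death and new treatment, so it does not replace the PD rate.
- **Week 12 ORR.** A reader might infer that early failures leave this endpoint in the same way. They generally do not: SAP 16.2.1 derives it as in 16.1.1, which counts unscheduled scans. Protocol 8.8 also expects missing Week 12 assessments to be rare. Only patients with death or new treatment and no prior post-baseline scan remain.
- **A composite row is a matter of preference.** Merging death and new treatment with PD would go beyond the IWG 2007 categories. This is accepted, and the fix keeps them apart.

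**Conclusion.** The point holds in a limited form. The available-data rule, without a provision that keeps an earlier central PD, can remove some early progressors from a named secondary endpoint. By the protocol's own account, the main expected reason for the missing result is new treatment for lack of efficacy or toxicity.

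At 6 affected patients of 154 the understatement of Week 28 PD is about 3.5 to 3.7 points; across 3 to 15 patients it is about 1.8 to 9.2 points. These sizes rest on assumed counts and on none of those patients being mapped to Week 28. A reader might take the loss to equal the full share of early failures. That is only an upper limit: the loss is k/N − s × [1/(N − k) − 1/N], which is below k/N whenever any Week 28 scan shows PD, and not every early failure is a progression.

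Only descriptive secondary summaries are affected. The equivalence test, sample size and power stand.

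**What to change.** In SAP 16.2.1 to 16.2.3:

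1. Report Week 28 CR, PR, SD and PD on the full FAS and PPS denominators. The PPS needs the rule too, because SAP 2.6 no longer excludes patients without a Week 28 assessment.
2. State that a centrally read PD before Week 28 remains PD at Week 28.
3. Add two separate rows: death or new follicular lymphoma treatment before the visit without PD, and not evaluable or missing.
4. State how SAP 5.3 applies to tumour assessments: which visit receives an early-discontinuation CT, whether patients who completed all four infusions are covered, and how unscheduled scans are used.
5. For Week 12 ORR, count as non-responders the few patients with death or new treatment and no prior post-baseline scan, for consistency with the primary analysis.

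The cost is SAP wording and a few table rows, with no new data. The response table will look slightly less favourable. The change should be made before unblinding.

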### **16.2.3. ANALYSIS OF SECONDARY EFFICACY VARIABLE(S)**

The ORR at Week 12 will be presented for each treatment group and the difference between treatment groups in ORR at Week 12 will be analyzed using the same method as the primary efficacy endpoint. The adjusted difference rate and corresponding 95% CI will be presented.

Descriptive statistics will be presented for the ORR and the overall tumor assessment (CR, PR, SD, PD) at Week 12 by treatment groups.

A bar-chart plot presenting the overall tumor response rate (CR, PR, SD and PD) and the ORR by treatment group will be provided for Week 12. A listing of the week 12 response assessments will also be presented.

For TTE, Kaplan-Meier curves will be calculated and displayed. Median survival times and the corresponding 95% CI will be provided using the Kaplan-Meier method. The estimated hazard ratio with 95% CI will be obtained from Cox regression model accounting for the same stratification factors with those of primary analyses, i.e. FLIPI-2 (low, intermediate and high risk). The occurrence of the events considered for the TTE and the TTE will be presented in a listing.

## **16.3. EXPLORATORY EFFICACY**

### **Subgroups**

The primary efficacy endpoint will be repeated for each of the following subgroup categories as exploratory efficacy analyses based on the FAS and the PPS.

- Region – EU, Others (including US)
- Age group – 18-60 years, >60 years
- Gender – Female, Male
- ADA status – Positive at any time up to Week 28, Negative at all time points

The same statistical method (as defined in Section 16.1.3) will be used for each subgroup category. The adjusted proportion difference in ORR and corresponding 95% CI according to the primary analysis will also be presented in a Forest plot. The interaction p-value for the subgroups being examined will be calculated based upon the full set of data (not subset for each subgroup category being examined), and will be based on primary CMH

---

Document:

Author:

Version Number:

Version Date:

Final v1.0

10Sep2019

Template No: CS\_TP\_BS016 Revision 4

Effective Date: 01Apr2016

Reference: CS\_WI\_BS005

model to which the variable for the subgroup being examined will be added as an additional stratification factor. The p-value will be calculated using Gail-Simon Test for Qualitative Interactions, specifying that we are interested in the subgroup variable risk differences.

As mentioned in section 3.3, additional exploratory subgroup analyses may be performed as ad hoc analyses if deemed necessary. The subgroups to be used for this analysis may be based on, but not limited to, the results of analysis of PK, PD, efficacy, safety, immunogenicity and concomitant medication.

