The adjusted difference in ORR between SAIT101 and MabThera[®] and its 95% Newcombe-Wilson CI will be calculated using the CMH weighted method accounting for appropriate stratification factors.

The following sensitivity analyses will be performed to explore the robustness of the primary efficacy result:

- The same adjusted analysis repeated in PPS and FAS with available data (no imputation)
- Unadjusted analysis for ORR (without covariates adjustment) in both the PP set and FAS with IUDR imputation

- A logistic regression model along with Delta method accounting for the same stratification factors will be performed in both the PP set and FAS with IUDR imputation
- Non-responder imputation (NRI) method will be used for patients without a response assessment at Week 28; patients without a response assessment at Week 28 will be handled as non-responders. The same adjusted analysis for NRI imputed ORR including stratification factors will be repeated for FAS
- A multiple imputation (MI) procedure using logistic regression method will be used to impute the missing primary efficacy results (responder versus non-responder) at Week 28, assuming data missing at random (MAR), to assess the impact of missing data and drop-outs. The same adjusted analysis for MI imputed ORR including stratification factors will be repeated for FAS

Further, expanded analysis on subgroup including stratification factors will be applied in an exploratory manner (i.e., region, etc.) and presented in a forest plot.

Efficacy response assessment (CR, PR, SD, and PD) at Week 12 will also be performed. For ORR at Week 12, the adjusted difference in ORR between SAIT101 and MabThera[®] and its 95% Newcombe-Wilson CI will be calculated using the CMH weighted method accounting for the same stratification factors with those of primary analysis. Previous studies^{3, 15} showed that patients without a response assessment at Week 12 are rare and therefore no missing data will be imputed for ORR at Week 12.

For TTE variables of secondary efficacy endpoints, Kaplan-Meier curves will be calculated and displayed. Median survival times and the corresponding 95% CI will be provided using the Kaplan-Meier method. The estimated hazard ratio with 95% CI will be obtained from Cox regression model accounting for the same stratification factors with those of primary analyses.

All efficacy variables will be summarized descriptively by treatment group for the FAS and PP Set.

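### The SAP's subgroup interaction p-value comes from a test for sign changes only, so subgroup effects that differ in size but not direction will almost never be flagged

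*SAP*

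**What the plan says.** SAP 16.3 (Subgroups) repeats the primary ORR analysis by region, age group, gender and ADA status, each with two levels, in the FAS and the PPS. Adjusted differences with 95% CIs go into a forest plot. On interaction it says: "The interaction p-value for the subgroups being examined will be calculated based upon the full set of data". The calculation starts from the primary CMH model, and "the variable for the subgroup being examined will be added as an additional stratification factor". The method sentence is "The p-value will be calculated using Gail-Simon Test for Qualitative Interactions", followed by the clause "specifying that we are interested in the subgroup variable risk differences".

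The primary model in SAP 16.1.3 is already stratified by FLIPI-2 at three levels. SAP 5.4 sets a default test level of 0.05 and gives no separate level for interaction. Protocol 8.8 makes the subgroup work exploratory: "expanded analysis on subgroup including stratification factors will be applied in an exploratory manner". Neither document plans a test of homogeneity of the risk differences.

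**The concern.** A reader who sees an interaction p-value beside a forest plot takes a large value as a sign that the effect is consistent across subgroups. Gail-Simon cannot give that assurance. Its null hypothesis is that all subgroup effects lie on the same side of zero, so no effect in one subgroup and a large deficit in the other is compatible with that null.

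In a biosimilar trial the natural question, for ADA status above all, is whether the difference between products varies in size. The planned p-value does not address it.

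There is also a specification gap. Adding the subgroup to a model stratified by FLIPI-2 gives 3 x 2 = 6 cells. The SAP does not say whether the test runs over those six cells or over two subgroup estimates with FLIPI-2 averaged out, and the two versions behave differently.

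**Working it through.** **Inputs from the documents.** 154 per arm, ORR 77% in both arms, margin ±16 points, two-sided 95% CI (SAP 2.3); FLIPI-2 with three levels (SAP 16.1.3); two levels per subgroup factor (SAP 16.3); level 0.05 (SAP 5.4).

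**Assumptions, not in the documents.** Equal subgroups of 77 per arm; FLIPI-2 split 40/35/25%, which gives cells of 31, 27 and 19 per arm in each subgroup.

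**The plan's own figure.** SE = √(2 × 0.77 × 0.23/154) = 0.0480. Power = 2Φ(0.16/0.0480 − 1.96) − 1 = 83.1%, against the stated 83%. The stated power reproduces. The SAP gives no power for the interaction test.

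**The test.** With estimates d and variances v, Q+ is the sum of d²/v over positive d, and Q− the same over negative d. The statistic is Q = min(Q+, Q−). For K groups, p = Σ Bin(h; K−1, ½) × P(χ²ₕ > Q). The 5% critical value is 2.71 for K = 2 and 7.48 for K = 6. With K = 2, rejection needs both estimates at least 1.645 SE from zero, in opposite directions. At 77% in both arms, SE = √(2 × 0.77 × 0.23/77) = 0.0678, so each must exceed about 11.2 points.

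**One observed result, two-subgroup version.** Differences of −2 and −25 points:

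- Both are negative, so Q+ = 0, Q = 0 and p = 1.
- v₁ = (0.77 × 0.23 + 0.75 × 0.25)/77 = 0.004735; v₂ = (0.77 × 0.23 + 0.52 × 0.48)/77 = 0.005542.
- Homogeneity: 0.23²/(0.004735 + 0.005542) = 5.15 on 1 df, p = 0.023.

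Q = 0 does not carry over to six cells, where individual cells can differ in sign by chance.

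**True differences of 0 and −20, two-subgroup version.**

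- Gail-Simon: the null subgroup must exceed +1.645 SE (probability 0.05). The other must fall below −1.645 SE: Φ(0.20/0.0740 − 1.645) = 0.85. The product is 4.3%.
- Homogeneity: Φ(0.20/√(0.00460 + 0.00548) − 1.96) = 51.3%.

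**Simulation, 40,000 trials per row, rejection at 0.05.**

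| True differences (points) | Gail-Simon, 6 cells | Gail-Simon, 2 subgroups | Homogeneity |
|---|---|---|---|
| 0 / −20 | 1.7% | 4.5% | 52% |
| −5 / −25 | 0.6% | 1.0% | 51% |
| 0 / −30 | 2.3% | 5.2% | 84% |
| +10 / −10 | 5.8% | 20% | 56% |
| +15 / −15 | 25% | 55% | 90% |
| +20 / −20 | 60% | 85% | 99% |
| No subgroup effect; FLIPI-2 effects +20/0/−30 | 59% | 0.5% | 5% |

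The first row differs from the closed-form values only by simulation and approximation error.

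**Sensitivity.** With a 70/30 subgroup split, a control ORR of 70%, or both, the pattern holds. For 0 / −30, the six-cell test flags 1.8–2.3% and homogeneity 74–81%. The false signal from FLIPI-2 alone ranges from 47% to 60%.

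**When the primary test succeeds.** Assume an 80/20 split with true differences of 0 and −25. The unstratified equivalence test passes in about 60% of trials. Among those, the two-subgroup Gail-Simon test flags about 6% and homogeneity 48%.

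**The case against.** The strongest reply is that little depends on this p-value. The analysis is exploratory, no decision rule uses it, and SAP 16.3 openly names the test as one for qualitative interactions. The forest plot gives an interval for every subgroup. In the −25-point example the unstratified Newcombe-Wilson interval runs from about −38.6 to −9.9, so a reader would see the problem. Whether equivalence holds within a subgroup is judged from that interval, not from any interaction p-value. A homogeneity test would itself miss a 20-point difference about half the time. All of this stands and limits the severity. It does not make a test with a ceiling near 5% a useful sole measure of interaction.

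Three stronger readings are tempting, and the documents do not support them:

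- *Every real subgroup difference would be reported as no interaction.* This holds only for differences in the same direction. A ±15-point crossover is detected in 55% (two subgroups) or 25% (six cells) of trials.
- *The test certainly runs over six cells.* Adding a stratum points that way, but the closing clause on the subgroup risk differences can mean a two-level test. What can be said is that the SAP does not state how FLIPI-2 is collapsed.
- *The SAP dropped a FLIPI-2 subgroup that the protocol promised.* Protocol 8.8 uses the same phrase about including stratification factors for covariate adjustment in its NRI and MI analyses, and its only subgroup example is region. Read as adjustment, SAP 16.3 complies.

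**Conclusion.** The point holds, at minor severity. The result labelled as the interaction p-value comes from a test with essentially no power above its nominal level unless effects change sign, and no homogeneity test accompanies it. For true differences of 0 and −20 points, detection is about 4% or 2% against about 51%; for ±15-point crossovers it is 55% or 25% against 90%.

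The handling of FLIPI-2 is unspecified. Under the six-cell version the test loses power for genuine subgroup crossovers, and it can credit a FLIPI-2 crossover to the subgroup, in about 59% of trials at +20/0/−30. Age over 60 is itself a FLIPI-2 factor (SAP 9), so the age cells would be entangled with the strata.

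The sizes rest on the assumed subgroup and FLIPI-2 splits. The same-direction result holds under either version of the test. The primary equivalence conclusion is unaffected.

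**What to change.** In SAP 16.3, define the interaction p-value as a homogeneity test of the FLIPI-2-adjusted risk differences between the two levels of each subgroup factor: (d₁ − d₂)²/(v₁ + v₂), referred to χ² on 1 df. Take d and v from the same adjusted analyses that feed the forest plot. Keep Gail-Simon, if wanted, as a supplement computed on the two subgroup-level estimates only and labelled as a test for qualitative interaction. Adding FLIPI-2 risk group to the forest plot is optional.

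The cost is a short SAP edit and a different test call, with no new data and no change to the primary analysis.
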